**HIDDEN AURICULAR AMYLOID DEPOSITS AND AORTIC STENOSIS:
CLINICAL AND PROGNOSTIC IMPLICATIONS IN AORTIC VALVE REPLACEMENT SURGERY**

February 20, 2023

Study Protocol

The Aortic-Ruti cohort is a prospective single center study of cardiovascular patients diagnosed with severe AS and with indication for isolated SAVR. Patient management was decided by the physicians, following recommended guidelines. The study also included a comparative analysis of two subgroups stratified by the presence or absence of amyloid deposits in intraoperative biopsy samples.

From November 2020 and November 2021, a total of 110 patients over 18 years of age, diagnosed with severe aortic stenosis by echocardiographic criteria, with indication for isolated aortic valve replacement and elective surgery, were included. The echocardiographic criteria for the diagnosis of severe AS were the following: average gradient greater than 40mmHg and/or maximum speed greater than 4m/s. Aortic valve area calculated by the continuity equation: the severity cut-off point established by the guidelines is less than 1cm² or set by the body surface index <0.6cm²/m². Those patients undergoing emergency surgery or combined surgery, with extra-cardiac disease with a prognosis of less than 365 days, with moderate-important alcoholism and abnormal laboratory values, were excluded.

During the surgery, atrium and ventricular septum biopsies were collected for histological and Visium Spatial Gene Expression analysis. Blood samples for biomarker analysis were obtained before the surgery, at discharge and at one month and one year of follow-up, centrifuged, and then serum and EDTA-plasma were stored at -80°C until assay.

Clinical and demographic characteristics were recorded at baseline, discharge, 1 month and 1 year.

Variables were collected prospectively. Intraoperative histological results were recorded, and a dedicated biomarker database was built, incorporating baseline and follow-up serum values collected at each visit.

Data were organized into five datasets per sub-cohort: Baseline, Follow-up, Biomarkers, EuroQuol Quality of Life test (EQ-5D-5L), and Histology.

Follow-up data analysis focused on one-year post-surgery results, except for EQ-5D-5L scores, where a mean of the three global scores (discharge, 1 month, and 1 year) was calculated per patient and compared between sub-cohorts.

Blood samples were collected at admission (n=105), discharge (n=84), one month (n=88), and one year (n=94) post-surgery. Serum and EDTA plasma were stored at -80 °C. Auricular and septal tissue samples were obtained during surgery in 70 patients and fixed in 4% paraformaldehyde before paraffin embedding.

Paraffin-embedded tissue sections (4 μ m) were stained using Congo Red, Sirius Red, and Trichrome techniques. For Congo Red staining, sections were treated with haematoxylin and a Congo Red solution, and positivity was confirmed by apple-green birefringence under polarized light. Sirius Red staining involved incubation with picrosirius to visualize collagen types I and III, appearing red/orange and apple green, respectively. Trichrome staining included fixation in Bowin's solution and sequential staining steps to differentiate tissue components, evaluated with a LEICA DMI6000B microscope.

Paraffin-embedded sections (4 μ m) were deparaffinized, rehydrated, and blocked with 5% horse serum in PBS-Tween and Triton X-100. Sections were incubated overnight at 4°C with primary antibodies against TTR (1:200), ANP (1:200), and troponin I (1:50). After washing, secondary antibodies (1:500) were applied for 45 minutes at room temperature. Following PBS

rinses, Congo Red staining and mounting were performed. Imaging was carried out using a Leica TCS SP5 confocal microscope.

Midregional Proatrial Natriuretic Peptide (MRproANP). MRproANP serum levels were measured with Midregional ProAtrial Natriuretic Peptide ELISA Kit (ABIN6975642; antibodies online; lot W17065241). The detection range and the minimum detectable dese are 39pmol/L – 2500pmol/L and 9.8pmol/L, respectively.

Meteorin-like (Mtrnl). Serum Mtrnl levels were measured with the Human Meteorin-like/METRNL DuoSet ELISA (DY7867-5; R&D; lot P300680). The detection range and the minimum detectable dese are 15.6 pmol/L – 1000 pg/mL.

Four tissue samples (Positive Congo Red, n=2; Negative Congo Red, n=2) were analyzed using the Visium Spatial Gene Expression system at the Josep Carreras Leukaemia Research Institute (IJC). RNA sequencing data was pre-processed and normalized using the SC Transform (SCT) method to correct for technical variability. Samples were integrated to identify spatially distinct clusters across conditions. Differential gene expression analysis was performed to classify cell populations, mapping them to known cell types such as fibroblasts, cardiomyocytes, endothelial cells, and immune cells. Data visualization was conducted using UMAP dimensionality reduction, and spatial cluster annotation was based on marker gene expression.

Statistical Analysis Plan

Categorical variables were summarized as counts and percentages, and continuous variables as mean \pm standard deviation or median (interquartile range), as appropriate. Changes from baseline to 1-year follow-up in clinical, imaging, and biomarker variables were assessed using linear regression models, with and without interaction terms for Congo Red status (positive vs. negative). Estimated marginal means were used to compare adjusted follow-up values.

Associations between Congo Red status and clinical outcomes, including hospital readmission and atrial fibrillation, were evaluated using conditional Poisson regression models adjusted for sex, age, LVEF, and baseline NT-proBNP. Left atrial size was additionally included in models assessing atrial fibrillation.

Further linear regression models were used to analyze the relationship between Congo Red status and log-transformed NT-proBNP, Metrnl, and EQ-5D-5L quality of life scores at 1 year, adjusting for key covariates. Model assumptions were verified, and 95% confidence intervals were reported. Analyses were performed using R software (v4.4.0).

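### Does giving NT-proBNP and Metrnl two unranked Congo Red analyses, one of change and one of the 1-year level, require a change to the plan?

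*Combined protocol and SAP*

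**What the plan says.** The first paragraph of the Statistical Analysis Plan covers change, with Congo Red status as the interacting factor: "Changes from baseline to 1-year follow-up in clinical, imaging, and biomarker variables were assessed using linear regression models, with and without interaction terms". It continues: "Estimated marginal means were used to compare adjusted follow-up values". It names no individual biomarker, does not say whether the response is the change or the 1-year value, gives no scale, and does not say what Congo Red status interacts with.

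The third paragraph adds a second set: "Further linear regression models were used to analyze the relationship between Congo Red status and log-transformed NT-proBNP, Metrnl" and "quality of life scores at 1 year, adjusting for key covariates". Those covariates are not listed. The only explicit list is for the Poisson models in the second paragraph: sex, age, LVEF and baseline NT-proBNP, with left atrial size added for atrial fibrillation.

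The Study Protocol describes "a comparative analysis of two subgroups stratified by the presence or absence of amyloid deposits in intraoperative biopsy samples", so the groups are observed and not allocated. It also says that "a dedicated biomarker database was built, incorporating baseline and follow-up serum values collected at each visit". On numbers, "Blood samples were collected at admission (n=105), discharge (n=84), one month (n=88), and one year (n=94) post-surgery" and "Auricular and septal tissue samples were obtained during surgery in 70 patients", out of 110 patients included.

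Neither part of the document states a primary endpoint, an alpha level, a power calculation or a ranking of analyses. The plan reports 95% confidence intervals.

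**The concern.** The natural reading is that NT-proBNP and Metrnl belong to the biomarker variables of the first paragraph. Metrnl is an assayed study marker, baseline NT-proBNP is used elsewhere in the plan, and the third paragraph presents its models as additional. Each marker then has at least two Congo Red comparisons.

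In a randomised comparison the two would have the same expected value. Here the groups are formed by a tissue finding, and amyloid-positive patients could well start from a different biomarker level. A comparison of raw changes and a comparison of 1-year values given baseline then estimate different quantities. This is the situation known as Lord's paradox, and either contrast can mislead, depending on how the marker behaves over time. If one shows a Congo Red difference and the other does not, and nothing says which is the result, the choice can be made after both are seen.

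**Working it through.** The document gives no figure to reproduce: no sample size, power, alpha or group-specific biomarker value. The check therefore asks when the two contrasts differ and by how much.

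**1. Algebra.** Let G be the baseline gap between Congo Red groups and b the within-group slope of the 1-year value on baseline.

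- Unadjusted change contrast: D1 - G, where D1 is the raw difference at 1 year.
- Baseline-adjusted 1-year contrast: D1 - bG.
- Adjusted minus change: (1-b)G.

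The contrasts coincide if G = 0 or b = 1. They also coincide if the change model includes the marker's own baseline: regressing Y1 - Y0 on group and Y0 gives the same group coefficient as regressing Y1 on group and Y0. Only the baseline slope moves, from b to b-1. This needs the same scale, other covariates and patients.

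**2. What the plan says about the pairing.** The (1-b)G result needs no own-baseline term in the first paragraph and an own-baseline term in the third. Neither is stated. Comparing adjusted follow-up values by marginal means fits a covariate-adjusted model at least as well as a raw change score. If the third paragraph borrows the Poisson covariates, its NT-proBNP model includes own baseline and its Metrnl model does not. If own baseline is left out and the 1-year value depends only on baseline, the 1-year contrast is +bG against a change contrast of -(1-b)G. With G = 0.5 SD and b = 0.5 these are +0.25 and -0.25 SD, which shows plainly that a level and a change are different questions.

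**3. Size under the least favourable stated pairing.** Assumptions, none from the document: 21/49 split of the 70 with tissue, equal SDs, b = rho = 0.3/0.5/0.7, a common log scale, two-sided 5% tests, 20,000 simulated runs.

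| Baseline gap | True situation | Exactly one significant (rho 0.3/0.5/0.7) |
|---|---|---|
| 0 | no effect | 5.6 / 4.3 / 3.6% |
| 0.3 SD | equal change | 13.3 / 9.5 / 6.6% |
| 0.3 SD | 1-year depends only on baseline | 10.9 / 8.7 / 5.9% |
| 0.5 SD | equal change | 27.0 / 18.3 / 11.4% |
| 0.5 SD | 1-year depends only on baseline | 20.3 / 16.0 / 11.0% |

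Repeat runs move these by up to about half a percentage point. The first row is the comparator: two correlated tests disagree sometimes even with no gap. At 0.3 SD and equal change, the excess is 13.3-5.6 = 7.7, 9.5-4.3 = 5.2 and 6.6-3.6 = 3.0 points, roughly half the printed rates.

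In standard errors, a 0.5 SD gap separates the contrasts by 0.35, 0.25 and 0.15 SD. The change contrast has a standard error of 0.307, 0.260 and 0.201, so the separation is 0.35/0.307 = 1.1, 0.25/0.260 = 1.0 and 0.15/0.201 = 0.7 standard errors. The 95% intervals would usually overlap heavily.

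**4. Multiplicity.** The two estimators correlate at sqrt((1+rho)/2) = 0.81/0.87/0.92. With no gap and no effect, at least one is significant in about 8/7/7% of runs per marker, against 5% for one contrast. Over two markers, if independent, that is 1-(1-0.067)^2 = 13% to 1-(1-0.08)^2 = 15%, against 1-0.95^2 = 9.8%. The document does not support or refute independence.

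**5. Patients.** If the blood counts are distinct patients among the 110, those with tissue and a 1-year sample number at least 70+94-110 = 54. Those with tissue and both samples number at least 70+94+105-220 = 49. The maximum is 70 in each case. Applying this to NT-proBNP is a further assumption, since the laboratory section describes assays only for MRproANP and Metrnl.

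**The case for a change.** The strongest argument for a change is that the text rules out none of the readings. No sentence shows that the two sets share a baseline adjustment, biopsy-defined groups give no reason to expect a zero gap, and a reader of a paper reporting only one contrast could not tell whether it had been chosen. Naming a leading contrast takes a few sentences.

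Part of this stands. The overlap is the natural reading, the algebra is right, and the response, interaction partner, scale and covariates are under-described.

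The step from there to a defect in the plan does not stand. A missing description is not a rule that gives a wrong answer. The first paragraph asks whether recovery after surgery differs by Congo Red status; the third asks whether the 1-year level does. Both are legitimate, and reporting both with intervals is sound in a cohort that ranks none of its analyses. The absence of ranking is general here and not peculiar to two markers.

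The remedy is also weaker than it looks. The plan is written in the past tense and already gives the one-year sample counts, so naming a leader now is a choice made after the data exist and cannot remove the selection it is meant to prevent. Nor is it free: an own-baseline-adjusted 1-year model is not stated in the plan, and putting both contrasts on one scale in the same patients may need refits.

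**Conclusion.** No change to the plan follows. This is a gap in description that analysts fill sensibly: the models have been fitted with some response, scale and covariate set, and a report that gives these with each estimate and the number of patients behind it tells the reader what each contrast means.

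The possible disagreement is real but conditional. It needs an unadjusted change model paired with an own-baseline-adjusted 1-year model, or a model without own baseline, together with a baseline gap and a slope below 1. None of these can be established from the document. On the assumed 21/49 split, discordant significance is about 4-6% with no gap, 6-13% at 0.3 SD and 11-27% at 0.5 SD, and the extra false-positive risk per marker is 2 to 3 percentage points. These figures rest on assumed split, correlations, gaps, equal SDs and a common log scale.

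The conclusion would change if the plan made a confirmatory Congo Red claim on one of these markers. It makes none.

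### Do the unnamed interaction partner and the unlisted covariates leave the Congo Red comparison of 1-year change undefined?

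*Combined protocol and SAP*

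**What the plan says.** The Study Protocol makes the comparison by amyloid status a stated part of the study: "The study also included a comparative analysis of two subgroups stratified by the presence or absence of amyloid deposits in intraoperative biopsy samples". The first paragraph of the Statistical Analysis Plan covers change from baseline to 1 year in clinical, imaging and biomarker variables. Its description of method is "biomarker variables were assessed using linear regression models, with and without interaction terms for Congo Red status (positive vs. negative", followed by "Estimated marginal means were used to compare adjusted follow-up values". It gives no model equation, does not say what Congo Red is crossed with, and does not name the adjusters.

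The second paragraph, on readmission and atrial fibrillation, does name its covariates: "conditional Poisson regression models adjusted for sex, age, LVEF, and baseline NT-proBNP". The third paragraph turns to models for "log-transformed NT-proBNP, Metrnl, and EQ-5D-5L quality of life scores at 1 year, adjusting for key covariates", and lists none.

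On data, the Study Protocol says "Data were organized into five datasets per sub-cohort: Baseline, Follow-up, Biomarkers", with quality of life and histology as the other two. The sampling text says "Blood samples were collected at admission (n=105), discharge (n=84), one month (n=88), and one year (n=94) post-surgery" and "Auricular and septal tissue samples were obtained during surgery in 70 patients".

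**The concern.** Read alone, the first-paragraph sentence fits several models. If Congo Red is crossed with the baseline value, the interaction tests whether the slope on baseline differs by group, not whether mean change differs. If visits are stacked and Congo Red is crossed with time, the interaction is the test of change. A reader given only an interaction p-value could take a null result on equal slopes to mean that recovery does not depend on amyloid status.

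The third paragraph has a separate gap. Congo Red status is not randomised, so a 1-year marker model that includes the same marker's admission value answers a different question from one that omits it. It is also unclear whether the log transform applies to NT-proBNP alone or to all three outcomes. The numbers are small, so the choice of model could affect a conclusion.

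**Working it through.** The documents give no sample size calculation, effect size, SD or alpha, so there is no figure of the plan's to reproduce. The check has four parts.

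**1. Which quantity answers the question.** Estimated marginal means of adjusted follow-up values come naturally from a model with one row per patient. Write Y0 for baseline, Y1 for the 1-year value and G for Congo Red:

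Y1 = a + b·Y0 + c·G + d·(Y0 × G) + error.

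At a common baseline m, the Congo Red difference in Y1 is c + d·m. Subtracting Y0 from both sides gives

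Y1 − Y0 = a + (b − 1)·Y0 + c·G + d·(Y0 × G) + error.

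Only the coefficient of Y0 changes. The Congo Red difference in change at baseline m is again c + d·m. So, with baseline in the model, the form of the outcome (change or 1-year value) does not affect the contrast. The coefficient d is a test of equal slopes; the marginal-means contrast is the comparison of change.

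**2. Does it matter whether the interaction is fitted?** The number of patients with tissue and both blood samples follows from the stated counts and the cohort of 110:

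- minimum: 70 + 94 + 105 − 2 × 110 = 49
- maximum: 70
- if missingness is independent: 70 × (94/110) × (105/110) = 57.1

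These limits apply to the biomarkers; they do not bound the clinical and imaging variables. The following are assumptions, not in the documents: 57 patients, 17 positive, unit SD, a 0.7 SD true difference in change, equal baselines, equal slopes, correlation rho of 0.3, 0.5 or 0.7. Rejection at two-sided 5% (4000 replicates):

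| Term | rho 0.3 | rho 0.5 | rho 0.7 |
|---|---|---|---|
| Marginal-means contrast at mean baseline, with interaction | 67.8% | 76.4% | 90.7% |
| Congo Red term, baseline-adjusted, no interaction | 67.9% | 77.3% | 90.9% |
| Change score on Congo Red | 51.9% | 64.7% | 86.4% |
| Baseline × Congo Red | 4.9% | 5.2% | 5.8% |

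The first two rows differ by at most 0.9 percentage points. The last row stays near 5% by construction: slopes were simulated equal, so a slope test can reject only at its nominal level. It confirms that d is a different test and shows no fault in the plan. With no true difference, all these one-row tests rejected between 3.9% and 5.7%, so their inference is valid. With 70 patients and 20 positive (3000 replicates), the baseline-adjusted term rejected 75%, 86% and 96%, and the change score 57%, 76% and 92%.

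**3. What ambiguity is left.** Let D be the baseline difference between groups. With equal slopes b, the baseline-adjusted contrast exceeds the difference in mean change by (1 − b) × D. In the simulation b = rho. For an assumed D of 0.5 SD the gap is:

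- rho 0.3: 0.7 × 0.5 = 0.35 SD
- rho 0.5: 0.5 × 0.5 = 0.25 SD
- rho 0.7: 0.3 × 0.5 = 0.15 SD

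With 70 patients, 20 positive and no difference in mean change, the baseline-adjusted term then rejected 26%, 18% and 13%, while the change score stayed near 5%. This is two estimands, not an error in either.

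**4. The third-paragraph covariates.** These belong to separate models and have no bearing on the change term. The paragraph immediately before names sex, age, LVEF and baseline NT-proBNP. Carrying that set forward is the natural reading; it would include NT-proBNP's own admission value but not that of Metrnl. The text does not confirm this, though it narrows the range.

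**The case for a change.** The strongest case for a change is that these sentences are complete, so neither redaction nor PDF extraction explains the omissions, and that the same SAP lists covariates for its Poisson models and could have done so here. At 49 to 70 biomarker pairs, and with groups that may differ at baseline, the choice between a change score and a baseline-adjusted value can move a result. A few sentences would settle it. All of that stands as a description of the gap.

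It does not establish a defect in the analysis. One-row intervals are valid, either covariate choice is legitimate, and biomarker change is already covered in the first paragraph. The remedy would be to record what was done.

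A second argument is that visits may have been stacked with no patient term. Standard errors would then be too large for a time by Congo Red term and too small for a Congo Red effect averaged over visits. Nothing in the documents shows that this was done. The separate Baseline and Follow-up datasets, and the biomarker database that holds values from every visit, describe storage and settle nothing either way. The wording on adjusted follow-up values points to one row per patient, so error rates for stacking would quantify a fault without evidence.

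**Conclusion.** No change to the plan follows. The SAP leaves out the interaction partner, the form of the outcome and the rows per patient for the change models. Separately, it leaves out the covariate list and the extent of the log transform for the 1-year models. An analyst fills the first gap sensibly from the next sentence of the SAP: the Congo Red contrast in estimated marginal means compares change at a common baseline, and under the assumptions above its power moves by at most 0.9 percentage points with or without a baseline interaction. The second gap is narrowed by the covariates named one paragraph earlier.

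The choice between change score and baseline-adjusted value remains open. It is worth 0.15 to 0.35 SD if the groups differ by an assumed 0.5 SD at baseline, and nothing on average if they do not. The SAP is a short account, in the past tense, of an observational cohort with no stated primary endpoint or alpha, so naming one result now would document a choice and not pre-specify it. This conclusion rests on reading the marginal-means sentence as a one-row, baseline-adjusted model. The text supports that reading but does not state it outright.

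### The atrial fibrillation (AF) outcome and its risk set are undefined and the AF model omits AF before surgery, so an imbalance in prior AF could move the Congo Red ratio away from 1 even if post-surgical AF is equal among patients with the same baseline AF status

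*Combined protocol and SAP*

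**What the plan says.** The second paragraph of the Statistical Analysis Plan covers "Associations between Congo Red status and clinical outcomes, including hospital readmission and atrial fibrillation". The method is "conditional Poisson regression models adjusted for sex, age, LVEF, and baseline NT-proBNP", and for AF one more covariate is listed: "Left atrial size was additionally included in models assessing atrial fibrillation". No stratum or matching variable is given for the conditional model.

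The Study Protocol section gives some context:

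- It separates the data by stage: "Data were organized into five datasets per sub-cohort: Baseline, Follow-up, Biomarkers, EuroQuol Quality of Life test (EQ-5D-5L), and Histology".
- It sets the horizon: "Follow-up data analysis focused on one-year post-surgery results".
- It lists four recording times: "Clinical and demographic characteristics were recorded at baseline, discharge, 1 month and 1 year". AF is not named among the baseline characteristics.
- The exclusions begin "Those patients undergoing emergency surgery or combined surgery, with extra-cardiac disease with a prognosis of less than 365 days" and go on to alcoholism and abnormal laboratory values. Prior AF is not among them.
- Atrial and septal tissue came from 70 of the 110 patients. The number positive and negative for Congo Red is not given.

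The title announces "CLINICAL AND PROGNOSTIC IMPLICATIONS IN AORTIC VALVE REPLACEMENT SURGERY".

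**The concern.** Two things are missing: what counts as an AF event, and who is at risk of one. Listing AF beside readmission, keeping separate baseline and follow-up datasets, and looking at one year all suggest AF recorded during follow-up. However, AF recorded at one year may be AF that the patient already had on admission. A time window does not make an event new.

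An association between amyloid and AF at any time is a legitimate clinical result. A prognostic claim needs more: AF arising or persisting after surgery has to be separated from AF already present. With no definition and no baseline AF term, a reader of the planned ratio cannot tell which of the two it reflects.

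**Working it through.** **No planned figure to reproduce.** The documents give no AF rate, ratio, power or sample-size calculation. Every rate below is an assumption chosen to show a range.

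**Notation.** p1 and p0 are the proportions with AF before surgery in Congo Red positives and negatives. r1 is the chance that a patient with prior AF is recorded with AF at follow-up. r0 is that chance in a patient without prior AF. r1 and r0 are the same in both Congo Red groups, so there is no Congo Red effect within either baseline AF stratum.

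**Case A: prior AF can count as an event.**

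Ratio = [p1·r1 + (1 − p1)·r0] / [p0·r1 + (1 − p0)·r0], with r1 = 0.7 or 0.9 and r0 = 0.15 or 0.25.

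- 10 points, lowest (30% vs 20%, r1 = 0.7, r0 = 0.25): (0.210 + 0.175) / (0.140 + 0.200) = 0.385 / 0.340 = 1.13.
- 10 points, highest (25% vs 15%, r1 = 0.9, r0 = 0.15): (0.2250 + 0.1125) / (0.1350 + 0.1275) = 0.3375 / 0.2625 = 1.29.
- Imbalance reversed: 0.2625 / 0.3375 = 0.78 to 0.340 / 0.385 = 0.88.
- 5 points: 0.3625 / 0.340 = 1.07 (25% vs 20%, r1 = 0.7, r0 = 0.25) to 0.3000 / 0.2625 = 1.14 (20% vs 15%, r1 = 0.9, r0 = 0.15).
- Equal prevalence: 1.00.

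**Case B: only new-onset AF counts, but patients with prior AF stay in the denominator.**

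Ratio = (1 − p1)·r0 / [(1 − p0)·r0] = (1 − p1) / (1 − p0).

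- 25% vs 15%: 0.75 / 0.85 = 0.88.
- 30% vs 20%: 0.70 / 0.80 = 0.88.

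The direction is opposite to Case A for the same imbalance.

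**Case C: only new-onset AF counts, and only patients free of AF at baseline are at risk.** Ratio = r0 / r0 = 1.00.

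**Do the planned covariates remove the shift?** This was simulated with ordinary Poisson regression and robust variance, because the conditioning is not explained. The settings were 70 patients split 35/35, the six planned terms, r1 and r0 as above, and prior AF going with larger left atrial size (+0.5 to +1.0 SD), higher NT-proBNP (+0.5 SD) and higher age (+0.3 SD). All of these are assumptions.

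- At 10 points, the planned model's median ratio was 1.12 to 1.30. A separate run gave 1.09 to 1.27.
- With baseline AF added, the ratio was 0.99 to 1.02 across the two runs.
- The estimate's 95% range spanned a factor of 1.83 to 2.41 each way under the planned model, and 1.77 to 2.44 with baseline AF.

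A large-sample run (25% vs 15%, every prior AF counted, 20% new-onset AF) tested stronger proxies. When prior AF moved left atrial size and NT-proBNP by 0, 0.5 or 1 SD, the planned model gave 1.25, 1.23 and 1.17. Under Case B it gave 0.88, 0.89 and 0.91. The covariates therefore absorb only part of the shift.

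At 70 patients, 40% of them positive, and the 0.5 SD setting, a nominal 5% test of the any-AF ratio rejected in 10.5% of runs at 25% vs 15%, against 4.6% at equal prevalence. With baseline AF in the model the figures were 6.4% and 6.6%.

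**Events available (70 patients, 15% to 30% prior AF).**

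- Fewest: 10.5 × 0.7 + 59.5 × 0.15 = 16.3.
- Most: 21 × 0.9 + 49 × 0.25 = 31.2.
- Per term: 2.7 to 5.2 with six terms, 2.3 to 4.5 with seven.
- New-onset only: 49 × 0.15 = 7.4 to 59.5 × 0.25 = 14.9 events, or 3.7 to 7.4 per term with two terms.

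**The case against.** The strongest reply is that the SAP claims only associations. Baseline AF may lie on the pathway from atrial amyloid to later AF, so leaving it out is a defensible choice if the question is any-timing AF. That stands: the omission is not in itself an error. It does not supply the missing definition, and it does not support a prognostic reading.

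The effect is also conditional and modest. There is no shift at equal prevalence, left atrial size and NT-proBNP take up part of any imbalance, and a 10-point imbalance moves the estimate by less than its sampling error. All of this stands.

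Three other replies carry less weight. The word conditional could mean that baseline AF is held fixed, but no conditioning set is given. The change-from-baseline models are linear and separate from the AF model. The Baseline dataset and the plan to report counts and percentages would allow a baseline AF table, but only if AF history was recorded.

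Two stronger readings are tempting, and neither is supported. A reader might infer that the ratio can move with no difference at all in AF after surgery. In Case A the post-surgical rates do differ (0.385 vs 0.340); what is equal is the risk within each baseline AF stratum. A reader might also infer that writing new-onset into the SAP settles the matter. Case B shows that it does not unless the denominator is stated too.

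**Conclusion.** The point holds in conditional form. Neither the AF event nor its risk set is defined, prior AF is not excluded, and the listed covariates leave it out. The planned ratio can therefore mix AF already present with AF after surgery, and cannot by itself carry the prognostic claim.

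Under the assumed rates, prior AF 10 points more frequent in Congo Red positives gives about 1.13 to 1.29 (Case A) or about 0.88 (Case B). These shifts are real but smaller than the interval's factor of roughly 1.8 to 2.4 each way.

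A reader might conclude that the AF result is biased. The documents do not show that: they give no baseline AF rate in either group, so the imbalance may be absent or may run the other way. The point is worth correcting because the correction is cheap, not because a large error has been shown.

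**What to change.** 1. State what counts as an AF event (any AF or new-onset AF) and which patients form the denominator.
2. Tabulate baseline AF by Congo Red status.
3. If any AF counts: keep the planned model and label it an any-timing association. For the prognostic claim, report beside it the same model with baseline AF (yes/no) added. Give new-onset AF among patients free of AF at baseline as a sensitivity analysis with few covariates, for example Congo Red plus one.
4. If only new-onset AF counts: restrict the risk set to patients free of AF at baseline rather than adding the covariate. Patients with prior AF could not have an event, so the baseline AF coefficient could not be estimated.

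**Cost.** This is one definition, one table row, and one further model with a sensitivity analysis, or a restriction. One more term is spent in at most 70 patients with few events, although the simulated interval width changed little. The new-onset analysis keeps about 49 to 60 patients (70 × 0.70 to 70 × 0.85), with an interval factor of about 2.6 to 4.0 each way in simulation (Congo Red plus left atrial size, 10-point imbalance). All of it relies on AF history having been recorded at baseline, which the documents do not confirm; if it was not, that limit should be stated. Because baseline AF may be on the pathway, the adjusted model answers a narrower question, so where any AF counts both models should be shown.
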